$$[a_{ih} \ b_{ih}]^T \sim \mathcal{N}(\mathbf{0}, \mathbf{G}), [a_h \ b_h \ c_h \ d_h]^T \sim \mathcal{N}(\mathbf{0}, \mathbf{H}), \epsilon_{ij} \sim \mathcal{N}(0, \sigma^2 \mathbf{I}_i), \text{ and } [a_i \ b_i]^T \perp [a_h \ b_h \ c_h \ d_h]^T \perp \epsilon_{ij}.$$

If individual site variance components in \mathbf{H} are negligible, then the associated random effects will be omitted to simplify the model. In the case that all \mathbf{H} components are negligible, we will revert to Equation (1) for the analysis.

Primary Objective #2: To evaluate the safety and tolerability of ibudilast versus placebo.

The main assessment of safety will involve a comparison of treatment-related SAEs across the two treatment groups. This will be assessed in two ways. First, the percentage of subjects who experience any treatment-related SAE in each group will be compared using a chi-square test. Then, the rates of treatment-related SAEs in each group will be compared using a Poisson regression model. We will also assess the values of laboratory assessments over time across the two groups using a LMM. To assess tolerability, the percentage of subjects who complete the entire treatment period will be compared across the two groups using a chi-square test. Appropriate constraints for baseline imbalance will be used in all statistical models.

Major Secondary Objectives: *To evaluate the activity of ibudilast at two years versus placebo, as measured by:*

- (1) *Diffusion tensor imaging (DTI) in descending pyramidal white matter tracts*
- (2) *Magnetization transfer ratio (MTR) imaging in normal-appearing brain tissue*
- (3) *Retinal nerve fiber thickness as measured by optical coherence tomography (OCT)*
- (4) *Cortical atrophy as measured by cortical longitudinal atrophy detection algorithm (CLADA)*

The secondary objectives will be analyzed using a model similar to that described above for the assessment of BPF. An exception is the OCT analysis will require additional random effects for eyes nested within patients. Additional details are provided below. The baseline intercepts will again be constrained to be equal to account for baseline imbalance.

Other Objectives

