7.2.1 Safety

The primary assessment of safety will compare the percentage of subjects in each group with:

- Treatment-emergent adverse events (TEAEs)
- Treatment-emergent serious adverse events (TESAEs)

The main assessment of safety and tolerability will involve a comparison of treatment-related AEs and SAEs across the two treatment groups. First, the percentage of subjects who experience any treatment-related AE in each group will be compared using the following logistic regression model:

$$\text{logit}(Y_i) = \beta_0 + \beta_1 x_{1i} + \beta_2 x_{2i} + \beta_3 x_{3i} + \epsilon_i$$

where

- Y_i represents an indicator of whether or not i^{th} subject had at least one treatment related AE.
- $x_{1i} = 1$ if i^{th} subject was thought to be receiving immunomodulation therapy at randomization (IFN/GA), and 0 if the subject was not thought to be receiving immunomodulation therapy
- $x_{2i} = 1$ if i^{th} subject was thought to have primary progressive MS at randomization, and 0 if the subject was thought to have secondary progressive MS
- $x_{3i} = 1$ if i^{th} subject was randomized to the Ibudilast group, and 0 if the subject was randomized to placebo group
- ϵ_i is random error for the i^{th} subject

To determine if the percentage of subjects having any treatment related AEs differ across treatment group we will test the following hypothesis:

$$H_0: \beta_3 = 0 \text{ vs. } H_A: \beta_3 \neq 0$$

If the null hypothesis is rejected, and $\beta_3 > 0$, we will conclude that Ibudilast was responsible for a significantly greater frequency of treatment-related AEs. Similarly, if $\beta_3 < 0$, we will conclude that Ibudilast was responsible for a significantly lower frequency of treatment-related AEs. In addition to an overall comparison, this hypothesis will be repeated for assessing the percentage of subjects having at least one treatment-related AE within each MedDRA system organ class (SOC). If there are significant differences between groups within any specific SOC, then additional tests will compare differences across groups for specific MedDRA preferred terms in order to further explore the cause of the observed differences.

In addition to the comparison of percentages in the manner described above, the rates of treatment-related AEs in each group will be compared using the following Poisson regression model:

$$\log\left(\frac{Y_i}{T_i}\right) = \beta_0 + \beta_1 x_{1i} + \beta_2 x_{2i} + \beta_3 x_{3i} + \epsilon_i$$

where

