- Y_i represents the number of treatment related SAEs experienced by the i^{th} subject.
- T_i represents the number of months between the date of randomization and the date of last follow-up for the i^{th} subject.
- $x_{1i} = 1$ if i^{th} subject was thought to be receiving immunomodulation therapy at randomization (IFN/GA), and 0 if the subject was not thought to be receiving immunomodulation therapy
- $x_{2i} = 1$ if i^{th} subject was thought to have primary progressive MS at randomization, and 0 if the subject was thought to have secondary progressive MS
- $x_{3i} = 1$ if i^{th} subject was randomized to the Ibudilast group, and 0 if the subject was randomized to placebo group
- ϵ_i is random error for the i^{th} subject

To determine if the rate of treatment related SAEs differ across treatment group we will test the following hypothesis:

$$H_0: \beta_3 = 0 \text{ vs. } H_A: \beta_3 \neq 0$$

If the null hypothesis is rejected, the direction of β_3 will indicate the direction of the observed effect. Values of $\beta_3 > 0$ indicate an increased rate of treatment-related AEs associated with the Ibudilast group, while values of $\beta_3 < 0$ indicate a decreased rate of treatment-related AEs associated with the Ibudilast group.

Treatment-related SAEs will be analyzed in the same manner described above. Additional safety analyses will also assess all treatment-emergent AEs, treatment-emergent SAEs, unanticipated SAEs, and treatment-related & unanticipated SAEs in a similar manner.

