10.2. Severity Assessment

The severity of AEs will be determined as described below:

- Mild (Grade 1): Ordinarily transient symptoms that do not influence performance of subject's daily activities. Treatment is not ordinarily indicated.
- Moderate (Grade 2): Marked symptoms sufficient to make the subject uncomfortable. Moderate influence on performance of subject's daily activities. Treatment may be necessary.
- Severe (Grade 3): Symptoms cause considerable discomfort. Substantial influence on subject's daily activities. May be unable to continue in the study and treatment may be necessary.
- Life-Threatening (Grade 4): Extreme limitation in activity, significant assistance required; significant and urgent medical/therapy intervention required. Hospitalization probable.
- Death (Grade 5): Death related to AE.

When changes in the intensity of an AE occur more frequently than once a day, the maximum intensity for the event should be noted for that day. Any change in grade of severity of signs and symptoms over a number of days will be captured by recording a new AE, with the amended severity grade and the date (and time, if known) of the change.

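### The SAP's rate model for treatment-related AEs defines its outcome as SAEs, and for AE counts plain Poisson variance makes no allowance for split records or overdispersion

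*Combined protocol and SAP*

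**What the plan says.** SAP 7.2.1 first compares the percentage of subjects with any treatment-related AE by logistic regression. It then adds that "the rates of treatment-related AEs in each group will be compared using the following Poisson regression model". Under that equation, Y_i "represents the number of treatment related SAEs experienced by the" subject. The hypothesis is introduced with "To determine if the rate of treatment related SAEs differ across treatment group", yet positive values of beta_3 are said to "indicate an increased rate of treatment-related AEs associated with the Ibudilast group". The section continues: "Treatment-related SAEs will be analyzed in the same manner described above". It then extends the approach to treatment-emergent AEs and SAEs and to unanticipated SAEs.

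Protocol 12.1.2 names one outcome for this type of model: "the rates of treatment-related SAEs in each group will be compared using a Poisson regression model".

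On recording, SAP 10.2 states: "Any change in grade of severity of signs and symptoms over a number of days will be captured by recording a new AE". Protocol 11.3.1 has the same rule. SAP 7.2.1 does not say whether such records are merged before Y_i is counted, and it names no dispersion parameter, negative binomial model or robust standard error. The equation has an extra term that "is random error for the" subject, with no distribution attached.

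**The concern.** SAP 2.2 places primary interest on treatment-related AEs, and this is the only model given for their rate. A programmer working from the definition of Y_i would count SAEs; one working from the introduction would count AEs. The results would be reported under the same label.

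For AE counts the variance also matters. Poisson regression takes the variance of each count to equal its mean. Several records from one episode, or subjects with different underlying AE rates, push the variance above the mean. The unadjusted standard error is then too small, and differences are declared too often in either direction. Splitting has a further effect: if grade changes are commoner in one arm, the ratio of record rates is no longer the ratio of episode rates, and no variance correction repairs that.

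**Working it through.** **Which outcome.** The steps of the model in SAP 7.2.1, in order:

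| Step | Outcome named |
|---|---|
| Introduction of the model | treatment-related AEs |
| Definition of Y_i | treatment-related SAEs |
| Hypothesis | treatment-related SAEs |
| Interpretation of beta_3 | treatment-related AEs |
| Sentence that follows | treatment-related SAEs, in the same way |

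The last row is redundant unless the model above it is for AEs. The introduction and the interpretation agree with that reading. The SAE wording matches protocol 12.1.2 and may have been carried over from there.

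**Variance.** The plan states no event rate, dispersion or power for this model, so it has no figure to reproduce. From the documents: 125 subjects per arm, and a two-sided hypothesis at 0.10 (SAP 6 and 7.2.1). Everything about dispersion is assumed.

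Let phi be variance divided by mean. The true standard error is sqrt(phi) times the Poisson one, and the actual type I error is 2 × [1 − Φ(1.645/√phi)].

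| phi | SE ratio | Type I error |
|---|---|---|
| 1.25 | 1.12 | 0.141 |
| 1.5 | 1.22 | 0.179 |
| 2 | 1.41 | 0.245 |
| 3 | 1.73 | 0.342 |

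*Differences between subjects.* If subject rates follow a gamma distribution with squared coefficient of variation k, then phi = 1 + k × mean. Protocol 4.6.3 gives treatment-related TEAEs over 12 months in the earlier relapsing MS trial: 12 among 103 on placebo and 26 among 99 on 60 mg/d. These are 0.117 and 0.263 per subject-year. Over 96 weeks (96/52 = 1.85 years) the means are 0.215 and 0.485. With assumed k = 1, phi is 1.22 and 1.48, and the type I error is 0.136 and 0.177.

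*Split records alone.* If a share f of AEs produces one extra record, phi = (1 + 3f)/(1 + f):

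| f (assumed) | phi | Type I error |
|---|---|---|
| 0.1 | 1.18 | 0.130 |
| 0.2 | 1.33 | 0.154 |
| 0.5 | 1.67 | 0.203 |
| 1.0 | 2.00 | 0.245 |

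*SAE counts.* With an assumed mean of 0.05 and k = 1, phi is 1.05 and the type I error 0.108.

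**Simulation.** The intended model was simulated under the null: 125 per arm, two stratification covariates, offset log T, 10% of subjects with shortened follow-up, 1,500 runs per scenario. The Monte Carlo standard error at 0.10 is √(0.1 × 0.9/1500) = 0.008.

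| Assumed counts | Poisson SE | Robust SE | Pearson-scaled SE |
|---|---|---|---|
| Mean 1, pure Poisson | 0.097 | 0.101 | 0.096 |
| Mean 1, f = 0.2 | 0.167 | 0.115 | 0.111 |
| Mean 1, k = 1 | 0.236 | 0.103 | 0.102 |
| Mean 1, k = 1, f = 0.2 | 0.321 | 0.113 | 0.109 |
| Mean 0.1, k = 1 (SAE-like) | 0.111 | 0.107 | 0.103 |

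A mean of 1 is above the 0.2 to 0.5 derived from the earlier trial. That trial used lower doses, so its rates are a rough anchor only.

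**The case against.** The strongest reply is that the intent is clear from the same section, so this is a slip of labelling. That largely stands. A reader might infer that the plan tests the wrong outcome or leaves AE rates untested. The documents do not support that: the text around the definition points to AEs, SAEs are a planned outcome in their own right, and the rate of all treatment-emergent AEs is also to be assessed. What remains is that the definition and the hypothesis, the two statements a programmer works from, name the other outcome.

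A reader might also infer that one model has both the wrong outcome and a badly understated standard error. The two hardly occur together. If Y_i is SAEs, the inflation is slight; the earlier trial's core period had 12 SAEs in 12 subjects. If Y_i is AEs, the outcome is right and only the variance question is left. Nor is a too-small standard error a certainty: it would be about right if repeat records were merged and subjects were homogeneous. The severity rule governs recording and is silent on counting for analysis.

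That log(Y_i/T_i) cannot be evaluated for a subject with no events is only loose notation, since the text names Poisson regression and a log link with an offset is plainly meant. The added error term could be read as a subject-level random effect that absorbs overdispersion. But it has no distribution, and the logistic equation carries the same term, so it specifies no such model. Protocol 12.1.2 promises residual checks for all analyses and possible generalized mixed models, but in the paragraph on imaging endpoints and at discretion.

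Finally, the primary safety comparison is of percentages of subjects with events. Repeat records cannot change it, nor the stated power for a 15-point difference, which concerns proportions.

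**Conclusion.** The point holds in two parts. The outcome contradiction is certain from the text and needs correcting, although the intended meaning can be recovered. The variance problem is conditional and concerns the intended AE count: plain Poisson regression is named, record splitting is built into data collection, and nothing in the analysis compensates for splitting or for differences between subjects.

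Its size rests on assumptions. Taking the earlier trial's related-AE rates with k = 1, dispersion is about 1.2 to 1.5 and the type I error about 0.14 to 0.18 against a nominal 0.10. With dispersion of 2 to 3 it would be about 0.25 to 0.34. For SAE counts it stays near 0.11. The change is worth making because this is a named analysis within a primary objective and the remedy is cheap.

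**What to change.** In SAP 7.2.1:

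- Define Y_i and the hypothesis as treatment-related AEs, and state a separate model of the same form for treatment-related SAEs.
- For the rate analysis, merge records that differ only by a change of grade and count one event per episode at its maximum grade. The recording rule in SAP 10.2 and protocol 11.3.1 can stay as it is.
- Write the model as a log-link count model with offset log(T_i) and no epsilon_i.
- Prespecify negative binomial regression, or Poisson regression with robust (sandwich) variance.

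The cost is SAP wording, a small derivation step to link records into episodes, and slightly wider intervals when counts are overdispersed. If counts are truly Poisson, little is lost: the simulated level was 0.101 with robust variance and 0.097 without.

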7.3.1. Follow-up Procedures Upon Discontinuation/Withdrawal

If a subject discontinues study medication for any reason, the subject will be encouraged to continue to be followed within the study, but on a reduced study visit schedule. Depending upon when the subject discontinued study drug, the reduced study visit schedule will include study visits at Week 24, 48, 72, and 96. The timing of all study visits will remain relative to the original baseline date. For subjects who discontinue study drug between regularly scheduled study visits, the subject should complete the next regularly scheduled study visit after study drug discontinuation, and then shift to the reduced study visit schedule. For subjects who discontinue study drug at a regularly scheduled study visit, the subject should shift immediately to the reduced study visit schedule. For subjects discontinuing study drug but remaining in the study for follow-up, study visits will occur on an approximate semi-annual basis until Week 96. Table 2 outlines the procedures and assessments to be conducted in subjects remaining in the study for follow-up but are off study medication. After study drug discontinuation, new-onset AEs will not be collected.

If a subject discontinues/withdraws prior to study completion and does not wish to continue follow-up within the study (i.e. return for semi-annual visits), then all assessments scheduled for the Early Withdrawal visit (Table 2) should be performed at the time of study discontinuation.

A termination CRF page should be completed for every subject who received study medication whether or not the subject completed the study. The reason for discontinuation should be indicated on the CRF. Any AEs that are present at the time of discontinuation/ withdrawal should be followed in accordance with the safety requirements outlined in Section 11.

For all subjects who complete the study on study medication, a follow-up visit (Week 100) will be conducted 4 weeks after the last visit to assess general health and adverse event status.

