8.8.2.8. Interval History

During each visit, adverse events and concomitant medications will be documented. For subjects who discontinue study medication and are followed on a semi-annual basis, adverse events that occur post-study drug discontinuation will not be collected. Only those adverse events that

occurred while on study drug will be followed until the event resolves or stabilizes or until all study related visits have been completed.

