8.8.2.12. Adverse Event (AE) Monitoring

The CSSPI or a qualified designee listed on Form FDA 1572 must assess the severity and relationship to study medication for all AEs (see Section 11.3).

All observed or volunteered AEs regardless of treatment group or suspected causal relationship to the investigational product(s) will be recorded on the AE page(s) of the CRF.

Each CSSPI and research team are responsible for identifying adverse events and reporting them through the DCC Online Adverse Event Reporting System.

For all AEs, the Investigator must pursue and obtain information adequate to determine the outcome of the AE and to assess whether it meets the criteria for classification as an SAE (see Section 11.3) requiring immediate notification to the Sponsor or its designated representative.

For all AEs, sufficient information should be obtained by the Investigator to determine the causality of the AE. The Investigator is required to assess causality and indicate that assessment on the CRF. For AEs with a causal relationship to the investigational product, follow-up by the Investigator is required until the event or its sequelae resolve or stabilize at a level acceptable to the Investigator, and Sponsor concurs with that assessment.

Adverse events (serious and non-serious) including all suspected unexpected serious adverse reactions (SUSARs) should be recorded on the CRF from the date of informed consent until the end of their participation in the study (i.e., the subject has discontinued or completed the follow-up visit).

The DCC will prepare aggregate reports of all adverse events (serious/not serious, expected/unexpected and relationship to study drug) for the Independent Medical Monitor (IMM) on a quarterly basis and the DSMB on a semi-annual basis, or as requested by either the Independent Medical Safety Monitor or the DSMB. In addition, all adverse events will be coded using the Medical Dictionary for Regulatory Affairs (MedDRA) system. A separate report detailing protocol compliance will also be available from the DCC for DSMB as requested.

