Subjects who prematurely discontinue study medication will continue to be followed on a semi-annual basis until the end of the study. For such subjects, adverse events will not be collected post study drug discontinuation. Existing AEs will be followed until the AE resolves or stabilizes.

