2.2. Safety

The primary assessment of safety will compare the percentage of subjects in each group with:

- Treatment-emergent adverse events (TEAEs)
- Treatment-emergent serious adverse events (TESAEs)

For the purposes of this study, a treatment-emergent adverse event (AE) is any untoward medical occurrence in a study subject who was administered a medicinal (investigational) product and which does not necessarily have a causal relationship with this treatment. An AE can therefore be any unfavorable and unintended sign (including a significant abnormal laboratory finding), symptom, or disease temporally associated with the use of a medicinal (investigational) product, whether or not considered related to the medicinal (investigational) product. Adverse events may include the onset of a new illness and the exacerbation of pre-existing conditions. Other untoward events occurring in the framework of a clinical study are also to be recorded as AEs (e.g., those occurring during treatment-free periods, including screening or post-treatment follow-up periods), in association with study-related procedures and assessments or under placebo.

One of the following categories should be selected based on medical judgment, considering the definitions below and all contributing factors:

- **Related**: A clinical event, including laboratory test abnormality, occurs in a plausible time relationship to treatment administration, and which cannot be explained by concurrent disease or other medications or chemicals. The response to withdrawal of the treatment (de-challenge) should be clinically plausible. The event must be definitive pharmacologically or phenomenologically, using a satisfactory re-challenge procedure if necessary.
- **Probably Related**: A clinical event, including laboratory test abnormality, occurs within a reasonable time sequence to administration of the treatment, unlikely to be attributed to concurrent disease or other medications or chemicals, and which follows a clinically reasonable response on withdrawal (dechallenge). Re-challenge information is not required to fulfill this definition.
- **Possibly Related**: A clinical event, including laboratory test abnormality, occurs within a reasonable time sequence to administration of the treatment, but which could also be explained by concurrent disease or other medications or chemicals. Information on treatment withdrawal may be lacking or unclear.

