10. SAFETY MONITORING

10.1. Assessment & Recording of Adverse Events

The clinical study site PI (CSSPI) or an authorized physician will assess all AEs for severity, relationship with study medication, and whether it meets the criteria for classification as an SAE, requiring immediate notification to the Sponsor or designee. These assessments will be made in accordance with the standard ratings detailed in the following sections. Each CSSPI and research team is responsible for identifying adverse events and reporting them through the DCC Online Adverse Event Reporting System (AERS).

Adverse events should be collected and recorded for each subject from the date the informed consent form was signed until the end of their participation in the study (i.e., the subject has discontinued or completed the study) through the follow-up visit with the exception of those who discontinue study medication during the study and are followed on a semi-annual basis. Subjects who discontinue study medication but continue follow-up within the study will not have AEs collected after study drug discontinuation. Only those AEs that occurred while on study drug that have not been resolved will be followed until resolution or stabilization.

Adverse events may be volunteered spontaneously by the study subject, or discovered by the study staff during physical examinations, or by asking an open, non-leading question such as, "How have you been feeling since you were last asked?" All AEs and any required remedial action will be recorded in the subject's source documentation and transcribed onto the appropriate CRF page for the study period indicated. The nature of AE, date (and time, if known) of AE onset, date (and time, if known) of AE outcome to date, severity, and action taken of the AE will be documented together with the CSSPIs or an authorized physician's assessment of the seriousness of the AE and causal relationship to study medication and/or study procedure (at the time of assessment).

All AEs should be recorded individually in the study subject's own words (verbatim) unless, in the opinion of the PI or an authorized physician, the AEs constitute components of a recognized condition, disease, or syndrome. In the latter case, the condition, disease, or syndrome should be named rather than each individual symptom. The AEs will subsequently be coded using the MedDRA.

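### The AE rate model in SAP 7.2.1 counts off-drug follow-up months in which new AEs are not collected, so AE rates are too low, more so in the arm with more such time

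*Combined protocol and SAP*

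**What the plan says.** SAP 7.2.1 compares AE rates with a Poisson model for log(Y_i/T_i), in which T_i "represents the number of months between the date of randomization and the date of last follow-up". The sign of beta_3 is read as a higher or lower rate on ibudilast. The same approach is then applied to treatment-related SAEs, to all treatment-emergent AEs and SAEs, and to unanticipated SAEs.

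A subject who stops study drug does not normally leave the study. Under Protocol 7.3.1 "the subject will be encouraged to continue to be followed within the study", with visits up to Week 96. SAP 6.2 keeps everyone who was randomized and took a dose in the safety population.

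AE collection stops earlier than follow-up:
- Protocol 7.3.1: "After study drug discontinuation, new-onset AEs will not be collected".
- Protocol 8.8.2.8: "adverse events that occur post-study drug discontinuation will not be collected".
- SAP 1: "For such subjects, adverse events will not be collected post study drug discontinuation".
- SAP 10.1, and likewise Protocol 11.4: "Subjects who discontinue study medication but continue follow-up within the study will not have AEs collected after study drug discontinuation".

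Protocol Table 2 agrees: the column for visits after drug discontinuation has no mark for AE review.

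Two places point the other way. Protocol 8.8.2.12 says AEs "should be recorded on the CRF from the date of informed consent until the end of their participation in the study", with no off-drug exception. The AE definition in SAP 2.2 (and Protocol 11.2) takes in "those occurring during treatment-free periods, including screening or post-treatment follow-up periods".

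**The concern.** In a rate model, person-time should cover only the period in which an event could have been counted. Here T_i continues after the date on which new events cease to be collected, and no section cuts it there or defines last follow-up as the last AE assessment. An arm whose subjects stop drug but stay in follow-up gains denominator with almost no events, and so looks safer per month.

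Safety is a primary objective, and the SAP draws a directional conclusion from beta_3. With unequal retained off-drug time, the rate result could disagree with the percentage result for a purely mechanical reason.

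**Working it through.** **Inputs.** From the documents: treatment to Week 96; off-drug follow-up to Week 96; a Week 100 visit with AE review for those completing on drug; 125 per arm; a two-sided test at 0.10. The plan states no AE rate, person-time or power for the rate model, so there is no figure of its own to reproduce. It gives no rate of stopping drug and staying in follow-up. The nearest figures are the 10% dropout in SAP 9.1 and the 86% two-year completion at 60 mg/d in the earlier MS trial (Protocol 4.6.3), that is 100 - 86 = 14% not completing. Neither is the quantity needed, so all stopping inputs below are assumptions.

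**Formula.** With a log(T_i) offset and treatment as the only covariate, each arm's estimated rate is total events divided by total T_i. Let p be the share stopping drug, s the mean stop week and f the share of stoppers who stay to Week 96. Per subject, in weeks:

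- AE-observed time O = 96(1 - p) + p·s
- SAP denominator T = 96(1 - p) + p[96f + s(1 - f)]
- recorded rate / true on-drug rate = O/T
- multiplier on the ibudilast/placebo ratio = (O/T for ibudilast) / (O/T for placebo)

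With s = 24, O = 96 - 72p. T is 96 if all stoppers stay and 96 - 36p if half stay. The O/T columns are for all staying.

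| Stopping, ibudilast vs placebo | O/T ibudilast | O/T placebo | Multiplier, all stay | Multiplier, half stay |
|---|---|---|---|---|
| 10% vs 10% | 88.80/96 = 0.925 | 0.925 | 1.00 | 1.00 |
| 14% vs 10% | 85.92/96 = 0.895 | 0.925 | 85.92/88.80 = 0.968 | (85.92/90.96)/(88.80/92.40) = 0.983 |
| 25% vs 15% | 78.0/96 = 0.813 | 85.2/96 = 0.888 | 78.0/85.2 = 0.915 | (78.0/87.0)/(85.2/90.6) = 0.953 |
| 40% vs 20% | 67.2/96 = 0.700 | 81.6/96 = 0.850 | 67.2/81.6 = 0.824 | (67.2/81.6)/(81.6/88.8) = 0.896 |

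Both arms' rates fall even where the ratio is right. If placebo has the higher stopping, the last two rows (all stay) become 1.092 and 1.214. If no stopper stays, T = O and the multiplier is 1.00. Letting completers run to Week 100 changes little: (81.0/99.0)/(88.6/99.4) = 0.918 and (69.6/98.4)/(84.8/99.2) = 0.827.

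Retention alone can also do it. With 20% stopping in both arms, s = 24, completers to Week 100, and 90% vs 50% of stoppers retained, mean T is 97.76 vs 92.00 weeks. The multiplier is 92.00/97.76 = 0.94, or 1.06 with the arms exchanged.

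**Effect on the test.** In 2,000 simulated trials (0.10 AEs per month, 30% vs 10% stopping, mean Week 24, all retained), a true ratio of 1.0 was estimated as 0.84 and rejected in 59% of trials. A true 1.2 was estimated as 1.01. Ending T_i with AE collection gave 1.00 (rejection about 10%) and 1.20. This assumes a constant rate and stopping unrelated to AEs.

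**Where that correction is not exact.**
- *Early clustering.* Take a Weeks 0-8 rate 10 times the later rate, a true ratio of 1, stopping at Week 8, and 40% vs 20% with all retained. Events in later-rate units are 80 per stopper and 80 + 88 = 168 per completer, so arm means are 132.8 and 150.4. As written: 132.8/150.4 = 0.883. With on-drug time: (132.8/60.8)/(150.4/78.4) = 1.139. A period factor cut at Week 8 gives 1.000.
- *Stopping triggered by AEs, with AE rates varying between subjects.* Two simulations (between-subject variance 1, true ratio 1, stopping about 37-39% vs 19-20%) gave 0.77-0.79 as written, 0.92-0.93 with on-drug time, and 0.89 with the period factor.

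**The case against.** **SAP 6.2 declares an intent-to-treat approach, so full follow-up time is intended.** That would be consistent only if off-drug events were collected. The label does not supply them.

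**For treatment-related AEs, which SAP 2.2 and 7.2.1 put first, few off-drug events would be expected even with full collection.** This stands. For those models the issue is mainly whether the rate is meant per on-drug month or per month since randomization. For all treatment-emergent events, where relatedness does not matter, the missing collection is a plain bias.

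**Off-drug entries are not strictly impossible.** Also true. A change of grade is recorded as a new AE (Protocol 11.3.1, SAP 10.2), and unresolved AEs are followed after the stop. A subject who stops between visits also attends the next regular visit. These can add some records; they do not amount to collecting AEs to Week 96.

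**The general passages imply collection throughout.** They are less specific than the stated off-drug exception. If they did govern, T_i as written would match the collection period, so the conflict must be settled either way.

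**The primary safety endpoints are percentages.** Correct: they use no T_i, discontinuation is tested separately, and no stopping rule or power statement rests on the rate. For treatment-related SAEs there may be almost no events to model, since no SAE in the earlier MS trial was judged related (Protocol synopsis).

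A reader might infer that the plan will make ibudilast look safer than it is. The documents do not show which arm will stop more or retain more stoppers, and the bias reverses with the arms. A reader might also infer that on-drug time restores the true ratio, or that a model by period must replace the planned one. The checks above support neither.

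**Conclusion.** The definition is wrong as written and should be fixed before analysis. Rates are understated in both arms, and the ratio is biased against showing harm in the arm with the larger off-drug share of T_i. If those shares are equal, or stoppers leave the study, the ratio is right.

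The size is unknown. Near the only figures the documents offer it is small (0.97 to 1.00). It reaches 0.82 to 0.92 only under larger assumed imbalances with full retention, and 0.90 to 0.95 in those cases if half the stoppers stay. All of these assume a constant AE rate and a mean stop at Week 24. The point bears mainly on the all-treatment-emergent AE and SAE rates.

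**What to change.** 1. **T_i.** End it when that subject's AE collection ends: permanent study drug discontinuation, the Week 100 visit for those completing on drug, or study exit if earlier. Temporary laboratory interruptions stay in T_i, because assessments continue on schedule (Protocol 8.6.2).
2. **Numerator.** Count only events with onset in that window, so that later grade changes logged as new AEs do not enter.
3. **Y_i.** Make it match the model. SAP 7.2.1 introduces the Poisson model for AEs but defines Y_i as SAEs; use AEs for the AE model and SAEs for the SAE model.
4. **Quarterly rates.** State the same denominator for the Medical Safety Monitor's tabulations in SAP 10.3, which name none.
5. **Reconcile** Protocol 8.8.2.12, and the post-treatment wording in Protocol 11.2 and SAP 2.2, with Protocol 7.3.1 and 11.4 and SAP 1 and 10.1.
6. **State the remaining limit.** If AEs trigger stopping and AE rates vary between subjects or cluster early, on-drug rates are closer to the truth than the current definition in most such cases, but not exact. Rates by period, for example cut at Week 8 when the daily dose becomes fixed, may be shown as an optional sensitivity analysis, not as the required model.

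The cost is SAP wording and one derived date per subject, plus a period variable if the sensitivity analysis is run. Dosing start and stop dates (Protocol 9.6) and AE onset dates (SAP 10.1) are already recorded, so no new data are needed.
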